4.4 End of Study Definition

The end of the study is defined as the date of the last visit of the last participant in the study.

A participant is considered to have completed the study if the participant has completed all study visits including Week 12 for Period 1, Week 16 for Period 2, or the ET visit.

5 STUDY POPULATION

Participants must meet all inclusion criteria and none of the exclusion criteria during screening. For eligibility purposes, abnormal laboratory or vital signs or ECG results may be repeated once during the Screening period or Day -1 (as applicable) for confirmation if an abnormal result is observed at the initial assessment.

Participants who do not meet all inclusion/exclusion criteria will be considered screen failures. Participants who fail screening may be rescreened; for handling of screen failures and rescreening, refer to [Section 5.3](#).

Deviations to recruitment and enrollment criteria, also known as eligibility waivers or exemptions, are not permitted.

5.1 Inclusion Criteria

Participants are eligible to be included in the study only if all of the following criteria apply:

1. Participant is capable of understanding and be willing to provide written informed consent prior to any study-related procedures.
 2. Participant is capable of understanding and adhering to all the requirements, procedures, instructions, and restrictions required by the protocol including scheduled visits, drug administration plan, laboratory tests, and likely to complete the study as planned.
 3. Healthy as determined by the Investigator, based on a medical evaluation, including medical history, concomitant medications, full physical examination, vital signs, laboratory tests, and ECGs at Screening and Day -1. Per Investigator's judgement, there should be no evidence of cardiovascular, pulmonary, endocrine, hepatic, biliary, gastrointestinal, neurological, hematological, immunological, metabolic, skeletal, renal, psychiatric disorders, or cancer within the past 5 years prior to Screening Visit (except localized or in situ cancer of the skin). Clinical abnormality or laboratory parameter(s) outside normal range must not be clinically significant or unlikely to introduce additional risk to the participant nor interfere with the study procedures nor the interpretation of any of the study assessments.
 4. Male or female healthy participants 18-65 years of age at Screening Visit.
 5. Participant has a body mass index (BMI) between 18 to 32 kg/m² inclusive at Screening and Day -1 Visits.
 6. Genetic testing confirming PI*MM.
 7. Participant has been a non-smoker for at least 1 year prior to screening and agrees to abstain from tobacco and nicotine containing products for the duration of the study.
 8. Women of childbearing potential (WOCBP) must be:
 - a. Non-pregnant as determined by a negative serum pregnancy test at Screening and negative highly sensitive urine pregnancy test on Day -1.
 - b. Non lactating.
-

- c. Agree to use a highly-effective method of contraception (as defined in [Section 10.4](#)) from **CCI** prior to Day 1 and for at least **CCI** following last study drug administration. Exception: Women exclusively engaging in same-sex sexual activities are not required to meet this criterion.
 - d. Must be willing to forgo ova (egg) donation for at least **CCI** following the last study drug administration.
9. Women of non-childbearing potential are defined as meeting at least 1 of the following criteria:
- a. At least 12 months post-menopausal and has an FSH >40 mIU/mL.
 - b. Surgically sterile, defined as having a documented bilateral oophorectomy, or hysterectomy.
10. Male participants must be willing to follow contraceptive requirements (as defined in [Section 10.4](#)) and should not impregnate anyone while they are in the study and for at least **CCI** following the last dose of study drug. In addition, participant must be willing to forgo sperm donation for at least **CCI** following the last dose of study drug. Men exclusively engaging in same-sex sexual activities are not required to meet this criterion.

5.2 Exclusion Criteria

Participants are excluded from the study if any of the following criteria apply:

- 1. Participant has a history of multiple drug allergies or of allergic reaction to an oligonucleotide or to N-acetylgalactosamine (GalNAc).
 - 2. Participant has a history of intolerance or any medical condition that might interfere with SC injection(s).
 - 3. History or signs or symptoms of severe (bacterial, viral, parasitic, or fungal) infection within 4 weeks prior to Screening or Day 1 Visits.
 - 4. History or signs or symptoms of an acute illness (including COVID-19) within 10 days prior to dosing on Day 1 Visit. Exception: mild seasonal allergies.
 - 5. Positive COVID-19 test at time of Screening (if required per site SOP) and at Day -1 Visit.
 - 6. Participant received a COVID-19 or any other vaccine within 14 days before dosing on Day -1 Visit or is scheduled for vaccination anytime during the study.
 - 7. Participant has total bilirubin > upper limit of normal (ULN) though participants with documented Gilbert's syndrome with normal conjugated bilirubin are eligible; aspartate transaminase (AST) and/or alanine transaminase (ALT) >ULN at Screening and Day -1.
 - 8. Participant has estimated glomerular filtration rate (eGFR) ≤ 60 ml/min/1.73mm² (calculated by the Cockcroft-Gault formula) at Screening and Day -1.
 - 9. Participant has a positive serology for hepatitis B or hepatitis C at Screening; participants with positive hepatitis B serology may be enrolled if there is evidence the participant received HBV immunization.
 - 10. Participant is known to be positive for human immunodeficiency virus (HIV) and/or positive serology for HIV 1/2 where testing is permitted per local regulations.
-

11. Participant has a history of regular alcohol consumption exceeding 14 standard drinks/week. 1 standard drink is equivalent to 14g ethanol or 5 US fluid ounces (fl oz) (150 mL) of wine (approximately 12% alcohol by volume), 12 fl oz (360 mL) of beer (approximately 5% alcohol by volume), or 1.5 fl oz (45mL) of hard liquor (approximately 40% alcohol by volume), within 1 year prior to the Screening Visit.
 12. Participant has a history of caffeine consumption exceeding 8 cups of coffee/day (1 cup = 8 fl oz [240mL]) within 14 days prior to first study dose, or consumption of any caffeine or chocolate containing products for 3 days prior to clinical research unit (CRU) admission. Caffeine-containing food and/or beverages (e.g., tea, cola) should be considered equivalent to coffee.
 13. Unwilling to abstain from alcohol for 48 hours prior to dosing at each of the dosing visits.
 14. Participant has a positive alcohol test at Screening and/or Day -1 Visits.
 15. Any prescribed or recreational substance use (irrespective of legality) within 6 months prior to screening or unwilling to refrain from such use for the duration of the study.
 16. Positive drug screen at Screening and/or Day -1 Visits.
 17. Positive cotinine test at Screening and/or Day -1 Visits.
 18. Use of prescription or non-prescription medications, including vitamin, dietary, and herbal supplements (including St John's Wort) within 7 days or 5 half-lives (whichever is longer) prior to the first dose of study treatment unless, in the opinion of the Investigator and Sponsor, the medication will not interfere with interpretation of study assessments. Contraception and hormone replacement therapy (HRT) are permitted. If needed, over-the-counter (OTC) medications such as paracetamol/acetaminophen may be used acutely.
 19. History of major surgery in the 3 months prior to Screening Visit and/or planned surgery for the duration of the study.
 20. Sustained hypertension defined as at least 2 repeated measurements at least 15 minutes apart of systolic pressure exceeding 130 mm Hg and/or diastolic pressure exceeding 80 mm Hg at Screening and/or Day -1 Visits.
 21. Supine pulse rate <45 beats per minute (bpm) or >100 bpm at Screening and/or Day -1 Visits.
 22. One or more of the following abnormal ECG findings at Screening and/or Day -1 Visits:
 - a. Second- or third-degree atrioventricular block
 - b. QRS >120 msec
 - c. QTcF >450 msec for males or >470 msec for females
 - d. PR interval >200 msec
 - e. Any rhythm other than sinus rhythm that is considered clinically significant by the Investigator.
 23. History of risk factors for Torsade de Pointes including unexplained syncope, known long QT syndrome, heart failure, myocardial infarction, angina, or clinically significant abnormal laboratory assessments including hypokalemia, hypercalcemia, or hypomagnesemia.
 24. Family history of long QT syndrome or Brugada syndrome.
-

25. Donation of blood or blood products in excess of 500 mL within 12 weeks prior to Screening Visit and/or unwilling to refrain from blood donation for the duration of the study.
26. Participant has any medical or social condition which in the opinion of the Investigator, would make the participant unsuitable for participation in the study, for study treatment, or could interfere with the assessments of safety or PK, or completion of the study.
27. Participant has received an investigational agent within 3 months or 5 half-lives (if known), or twice the duration of biological effect (if known), whichever is longer, before Screening, or who is in follow-up of another clinical study of an investigational agent at the time of the Screening Visit.
28. Exposure to more than 4 new chemical entities within 12 months prior to the Day 1 Visit.
29. Prior treatment with any oligonucleotide or small interfering RNA within 12 months prior to the Day 1 Visit.
30. Participant is directly or indirectly involved in the conduct and administration of this trial as an Investigator, sub-investigator, trial coordinator, or other trial staff member, or the participant is a first-degree family member, significant other, or relative residing with one of the above persons involved directly or indirectly in the trial.

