^a Screening assessments can occur on multiple days, provided they are within the Day -28 up to Day -2 Screening period.

^b Negative serum pregnancy test at Screening for women of childbearing potential (WOCBP). Negative highly sensitive urine pregnancy test documented for WOCBP on Day -1.

^c FSH only to confirm non-childbearing potential.

^d COVID-19 testing if required per site SOPs.

^e Safety laboratory tests include hematology, clinical chemistry, coagulation and urinalysis as noted in [Table 11](#). Note that for urinalysis, abnormal results on dipstick or urinalysis should lead to laboratory urinalysis testing and/or urine microscopy. Any specific safety labs indicated in [Table 2](#) will be collected according to the schedule in that table. When applicable and feasible, blood sampling should follow evaluations of vital signs and ECGs to reduce any impact on these measurements.

^f Specific time points for PK and select laboratory assessments provided in [Table 2](#) and [Table 3](#). Participants should stay in the clinic for 48 hours after dose to complete assessments.

^g Full physical examination includes (at a minimum): alertness and orientation, general appearance, skin, head, eyes, ears, nose, throat, lungs, cardiovascular, gastrointestinal, musculoskeletal, and neurologic systems. Symptom-directed physical exams to be performed by visit as necessary.

^h Height at Screening will be used for BMI calculations at all visits.

ⁱ Vital signs will be taken with the participant in the supine position after ≥5 minutes of rest. Temperature, respiratory rate, and percent oxygen saturation in the blood (SpO₂) are measured once per time point. Blood pressure (systolic and diastolic) and pulse: measured ≤30 minutes pre-dose and 1 hr (±10 min), 2 hr (±10 min), 4 hr (±20 min), 12 hr (±1 hr) post dose on Day 1 and once at all other noted visits.

^j Continuous digital ECG monitoring for at least 48 hours from Day -1 through Day 2; leads may be disconnected for ~20 minutes at 24 hours after dosing to allow for participant cleansing. Additional triplicate 12-lead ECGs are specified in [Table 4](#). Participant must rest quietly for ≥5 minutes prior to triplicate ECGs.

^k For drug screen panel, see [Table 11](#) other screening tests.

Table 2 Plasma PK and Selected Laboratory Time Points (Period 1)

Visit	2											3	4	5 through 14
Study Day/ Specific Time/ Window	Day 1								Day 2		Day 3	Day 8	Day 15	Weeks 3 through 12

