4.3 Justification for Dose

Initial Dose

As described in the International Council for Harmonization (ICH) M3(R2) guideline, the selection of the first-in-human (FIH) dose and dose escalation plan will not be higher than that supported by NOAELs from the 5-week interim data of the GLP 13-week repeat dose toxicity studies in mice and cynomolgus monkeys. Selected doses were based on the totality of the data for both mouse and cynomolgus monkey, including the NOAEL provided by the GLP toxicity studies, projected pharmacologically active dose and assessment for potential QTc prolongation risks. The initial dose was selected using the most relevant approaches described in:

- US Food and Drug Administration (USFDA) guidance for industry: [Estimating the Maximum Safe Starting Dose in Initial Clinical Trials for Therapeutics in Adult Healthy Volunteers](#) (2005).
- European Medicines Evaluation Agency (EMA) [Guideline on strategies to identify and mitigate risks for first-in-human and early clinical trials with investigational medicinal products](#) (2017)

CCI [REDACTED] Two interspecies scaling approaches were used for HED and safety margin projection, a conservative approach based on body surface area (BSA) scaling ([FDA, 2005](#)), as well as an empirical approach based on body weight supported by literature, which showed a 1:1 body-weight-based conversion factor from monkey to human and an approximately 1:7 body-weight-based conversion factor from mouse to human for plasma exposure ([Nanavati et al., 2021](#); [Wang et al., 2019](#)).

The pharmacological activities of WVE-006 are not expected in HV CCI [REDACTED]

Dose Escalation

CCI

The planned initial dose for Period 1 is 30 mg (Period 1, Cohort 1). Subsequent dose levels will be determined by the DEC and DMC based on previous Period 1 cohort data and will not exceed a CCI increase of the prior dose. The maximum dose will not exceed the limit specified in [Section 4.1.2](#). Dosing decisions will be communicated directly to the site.

CCI

If adequate safety and tolerability is observed in the initial dose cohorts (Cohorts 1 to 5) and no cohort stopping criterion was met, an optional cohort (Cohort 6) may be conducted in order to characterize the safety, tolerability, PK and the relationship between drug concentration and QTc prolongation at an appropriate dose.

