10.2 Appendix 2: Clinical Laboratory Tests

- The tests detailed in [Table 11](#) will be performed per the Sponsor provided Laboratory Manual.
- Laboratory tests will be done at the time points per the SoA in [Section 1.3](#). Urine dipstick and urine pregnancy test results will be recorded in the participant's medical record and corresponding eCRFs.
- Protocol-specific laboratory value requirements for inclusion or exclusion of participants are detailed in [Section 5](#) of the protocol.
- Additional tests may be performed at any time during the study as determined necessary by the Investigator or required by local regulations.
- Investigators must document their review of each laboratory safety report. Any laboratory result considered by the Investigator as clinically significant must be documented as AE and graded per CTCAE criteria. (see [Section 10.3](#)).

Table 11 Detailed Clinical Laboratory Tests

Laboratory Tests	Parameters	
Hematology¹	
 • Platelet count 	
	
 • Red blood cell (RBC) count 	
	
 – RBC indices 	
 – Mean corpuscular volume (MCV) – Mean corpuscular hemoglobin (MCH) – Mean corpuscular hemoglobin concentration (MCHC) – %Reticulocytes
	
 • White blood cell (WBC) count with differential: 	
 – Neutrophils – Lymphocytes – Monocytes – Eosinophils – Basophils
	
 • Hemoglobin • Hematocrit 	
	
 • Markers of Inflammation 	
 – C-reactive protein – Complement (C3, Bb, C3a, and sC5b9)
Clinical chemistry²	
 • Blood urea nitrogen (BUN) • Potassium • Creatinine • Sodium • Gamma glutamyl transferase • Chloride • Bicarbonate • Blood glucose 	
 • Aspartate transaminase (AST) • Alanine transaminase (ALT) • Alkaline phosphatase • Total Bilirubin (direct bilirubin if Total Bilirubin is elevated) • Creatine phosphokinase • Total protein • Albumin¹ • Glutamate dehydrogenase (GLDH)

Coagulation¹	
 • Prothrombin time or international normalized ratio (INR) (per site's laboratory standards) • Activated partial thromboplastin time (aPTT) • Fibrinogen

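### Exclusion 23 names three electrolyte abnormalities as Torsade de Pointes risk factors, but the laboratory panel schedules a test for only one of them, potassium

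*Combined protocol and SAP*

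**What the plan says.** Criterion 23 in Section 5.2 opens with "History of risk factors for Torsade de Pointes including unexplained syncope, known long QT syndrome", lists several cardiac conditions, and ends with "clinically significant abnormal laboratory assessments including hypokalemia, hypercalcemia, or hypomagnesemia". The synopsis (Section 1.1) has the same wording.

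The footnotes to the Schedule of Assessments (Table 1 for Period 1, Table 5 for Period 2) define the safety laboratory tests by reference: "Safety laboratory tests include hematology, clinical chemistry, coagulation and urinalysis as noted in" Table 11. In Table 1 these tests fall at Screening, Day -1, Day 2, Day 3 and each follow-up visit. The corresponding row of Table 5 is unreadable in the available text, but its footnote points to the same panel.

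The first column of the Table 11 chemistry panel begins with blood urea nitrogen and continues "Potassium • Creatinine • Sodium • Gamma glutamyl transferase • Chloride • Bicarbonate • Blood glucose". The second column holds the liver enzymes, total bilirubin, then "Creatine phosphokinase • Total protein", albumin and glutamate dehydrogenase.

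Appendix 2 (Section 10.2) also provides that "Additional tests may be performed at any time during the study as determined necessary by the Investigator", or where local regulations require them.

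On QTc, Table 8 includes QTcF change in the primary endpoint. Section 4.3 describes an optional Cohort 6 that would characterize, among other things, "the relationship between drug concentration and QTc prolongation at an appropriate dose". Section 9.3.6 plans a QTcF and WVE-006 correlation when appropriate.

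**The concern.** An eligibility criterion that rests on a laboratory finding needs a laboratory result behind it. Here the protocol names three electrolyte findings and schedules the measurement for one.

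Two things are at stake. The first is uniform eligibility. The synopsis allows up to 4 clinical research units. If calcium and magnesium are checked only where an investigator thinks of it, the same volunteer could be excluded at one unit and enrolled at another, and the record would not show which participants had been tested.

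The second is interpretation. The protocol itself treats these electrolytes as relevant to Torsade de Pointes risk. If a participant has an outlying QTcF value after dosing, the scheduled data contain no calcium or magnesium result to set beside it. With up to 6 active participants per cohort, a single unusual value weighs heavily in a descriptive summary.

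**Working it through.** There is no planned figure to reproduce, because no sample size, power or error rate is involved. The check is a cross-read.

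**Step 1. Match the criterion to the panel.**

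| Condition named in criterion 23 | Analyte needed | In Table 11 chemistry? |
|---|---|---|
| Hypokalemia | Potassium | Yes |
| Hypercalcemia | Calcium | Not listed |
| Hypomagnesemia | Magnesium | Not listed |

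Table 11 chemistry has 8 + 8 = 16 visible entries: urea nitrogen, potassium, creatinine, sodium, gamma glutamyl transferase, chloride, bicarbonate, glucose; AST, ALT, alkaline phosphatase, total bilirubin, creatine phosphokinase, total protein, albumin and glutamate dehydrogenase. Conditions without a scheduled analyte: 3 − 1 = 2 of 3.

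**Step 2. Look for the analytes elsewhere.** The hematology, coagulation, urinalysis and other screening sections of Table 11 contain neither. Tables 2 and 6 add timed samples for blood count, C-reactive protein, fibrinogen, coagulation, albumin, complement and cytokines, but no calcium or magnesium.

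**Step 3. Ask what the site must do with criterion 23.** Section 8 requires Screening assessments to satisfy the Section 5 criteria. Section 8.1.3 has the Investigator confirm all criteria from the Screening laboratory results together with other assessments. Section 10.2 points to Section 5 for the laboratory requirements on eligibility. Sections 5 and 10.5.2 allow no waivers. The site must therefore confirm this criterion, yet the schedule does not generate two of the results it refers to.

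**Step 4. Compare the other laboratory-based criteria.**

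| Criterion | Test in Table 11 |
|---|---|
| Inclusion 6, genotype | *SERPINA1* genotyping |
| Inclusion 8, pregnancy | Serum or urine hCG |
| Inclusion 9, post-menopausal status | FSH |
| Exclusion 7, bilirubin, AST, ALT | All three, with direct bilirubin if total is raised |
| Exclusion 8, eGFR | Creatinine |
| Exclusions 9 and 10, hepatitis and HIV | Serology with reflex testing for hepatitis |
| Exclusions 14, 16 and 17, alcohol, drugs, cotinine | All three |
| Exclusion 23, electrolytes | Potassium only |

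In this list every named laboratory condition has its test except the calcium and magnesium parts of criterion 23. That pattern suggests an omission rather than a decision to rely on history.

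**Step 5. Size.** The maximum enrolment to which the gap applies is 40 (Period 1) + 8 (Period 2) + 8 (optional cohort) = 56. One participant in an active group of 6 is 1/6 = 16.7% of that group. This percentage only shows the weight of one participant; it applies if such a participant exists and is on active drug. The documents give no rate for these abnormalities, so no expected count is calculated.

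**The case against.** The strongest reply is that the criterion still has force without a scheduled test.

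- It is framed as a history of risk factors. A medical history is taken at Screening (Section 8.1.1), and the Investigator may order extra tests at any time.
- Inclusion 3 already requires that laboratory values outside the normal range not be clinically significant. Exclusion 26 gives further discretion.
- Exclusion 22 screens QTcF directly at Screening and Day -1, with limits of 450 msec for men and 470 msec for women.
- Tables 4 and 7 place three triplicate ECG time points before the first dose, baseline is the last pre-dose value (Section 9.3.1), and there is a placebo group. A stable disturbance present before dosing is therefore largely carried in the participant's own baseline. Only a change after dosing could resemble a drug effect, and a screening criterion would not prevent that.

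Most of this stands, and it limits the point. A reader might infer that two of the three electrolyte checks do not work, that calcium and magnesium are never measured, or that a QTcF outlier could not be investigated. The documents do not support any of these: history can exclude a participant with a known abnormality, and a test can be ordered after an unexpected ECG.

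The reply does not supply a required test applied in the same way at every unit. History finds only what is already known, whereas the criterion refers to laboratory assessments. Discretionary testing prompted by an ECG finding also leaves no scheduled pre-dose value for comparison.

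Two cautions concern the evidence. The chemistry heading in Table 11 carries a superscript 2, but only note 1 appears beneath the table in the available text. The tests are also run under a Laboratory Manual that is not part of the documents. Neither shows that calcium or magnesium is measured, but a lost note cannot be excluded.

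**Conclusion.** The mismatch is real. Two of the three electrolyte conditions in criterion 23 have no scheduled test in the visible panel, so they depend on medical history or on testing at the Investigator's discretion, which may vary between units. It is worth correcting because QTc is a stated interest of the trial and the correction is cheap. It does not threaten the trial: no sample size, error rate or planned analysis changes.

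This rests on two assumptions: that Table 11 as visible is the full chemistry panel, and that the number of healthy volunteers affected is small. The second is a judgement about a screened healthy population, not a figure from the documents.

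A reader might also infer that the calcium term points the wrong way, so that the criterion excludes high calcium and lets low calcium in. The documents do not establish this. The synopsis and Section 5.2 use the same word, and nothing in the protocol says which calcium abnormality carries the risk; the argument would rest on outside knowledge. The wording is also an open list of examples, and inclusion 3 separately covers any clinically significant abnormality, so a known low calcium is not admitted by this text. What remains is a query to the sponsor about the intended term.

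**What to change.** 1. Reconcile criterion 23 with Table 11 by adding serum calcium and magnesium to the clinical chemistry panel. They would then be reported at Screening, Day -1 and each scheduled safety chemistry sample. Every unit could apply the criterion in the same way, and an outlying QTcF value could be read beside the participant's own electrolyte results before and after dosing.
2. Ask the sponsor to confirm that hypercalcemia is the term intended in both the synopsis and Section 5.2.
3. Check whether note 2 to the chemistry heading exists in the source document, and restore it if so. If it already provides for calcium and magnesium, item 1 falls away.

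If the sponsor means these conditions to be judged from history alone, the criterion should say so. That would remove the inconsistency but would add nothing for QTcF interpretation.

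The cost of item 1 is two analytes on samples already drawn, with no extra visit or venepuncture. The downside is a small laboratory charge and possibly a few more screen failures.
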